#### *Time from symptom onset to death*

Data assessing the time course from onset of symptoms to death or time to recovery remain limited and generally do not include vital sign measures in the community. After onset of symptoms, the highest probability of death occurs just under 12 days, so there may be time after symptom onset to predict the likelihood of clinical decline and guide clinical intervention in many patients.

Currently, predictors of hospitalization across the lifespan remain general, demographic and largely intuitive. For example, individuals with advanced disease or multi-morbidity are at increased risk for poor outcomes when infected with COVID-19. A major goal of this work is to identify novel digital biomarkers that will enable early identification of patients who are likely to have severe disease while still in the community. This early identification could allow for more timely and aggressive supportive care, potentially reducing more severe disease and poor outcomes.

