## **Stage 2**

### *Testing Stage – Expansion for Model Creation or Validation*

To assess the algorithm performance, algorithm testing on a total of 1,000 participants will be conducted. This cohort of 1,000 testing participants will be held entirely separate from the

training participants to minimize data snooping bias in the study. In machine learning, it is typical to obtain initial testing cohort results to determine if the model created from the training data is performing well. After the first 100 participants in the testing cohort are monitored for 30 days, the algorithm will be tested for understanding initial performance. As more participants are recruited into the study, follow-up algorithm testing will occur for each 100 participants that are added to the testing cohort.

Although the outcome of the participants in the validation set is known, the outcomes will be initially ignored, as if researchers did not know participant outcome. This simulates what researchers know about a participant, preceding the participant's outcome. The testing participants' collected variables (demographic, medical history, continuous data from wearable, and symptom data) will be run through the developed Bayes network algorithm and comparison models. The algorithm will return probabilities of the study outcomes. The algorithm's probabilities will then be compared with the true outcome of the participant recorded by the study team.

The differences between the algorithm prediction and participant's true outcome will be used to calculate performance metrics such as positive predictive value (PPV), area under the curve/receiver operating characteristic (AUC/ROC), and Brier scores. The final part of algorithm validation will be calibration analysis, sensitivity analysis, and determining any subpopulations that may have had poor predictive performance.

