### 4. Introduction

#### 4.1. Preface

In the proposed research, we will use Current Health's remote monitoring wearable device to create novel algorithms to help us predict the progression and severity of COVID-19 in individuals that have recently become infected in the community. Risk scores based on demographics, or for patients in hospital, already exist. However, by using continuous remote patient monitoring, in combination with machine learning and data analysis, we hope to predict the risk of an individual infected with COVID-19 requiring hospitalization, intensive care unit (ICU) treatment, or death based on their vital signs while still in the community.

Using a hospital-grade home-based, remote monitoring wearable gives us the opportunity to create a unique and extremely useful tool in predicting and managing the clinical effects of the COVID-19 pandemic. Our algorithm might bridge the gap between demographic models and in-hospital models of disease progression by providing real-time data from the community. If we are successful, this tool could be made available immediately to enable better resource allocation for patients after diagnosis. In addition, it enables patient-centered management, increasing confidence for low and high-risk patients, and those managing their care. The results of this research will provide a database that can be used in future trials to assess treatment efficacy and offer the potential for rapid algorithm iteration in the event of a future pandemic.

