# 5. Study Objectives and Endpoints and Hypotheses

## 5.1. Study Objectives, Endpoints, and Outcomes

The overall objective of this study is to train, develop, validate and release a digital biomarker-based algorithm that, in COVID-19 PCR or antigen positive participants, within 30 days of a positive test:

1. Primary Outcomes:
  - a. Predicts likelihood of requiring a stay in hospital of at least 24 hours
  - b. Predicts likelihood of recovery from COVID-19 defined as:
    - i. For asymptomatic participants: 14 days without symptoms following positive test
    - ii. For symptomatic: at least 14 days since onset of symptoms, with the last three days symptom free
2. Secondary Outcomes:
  - a. Predicts likelihood of being admitted to ICU for either non-invasive (CPAP, BiPAP, high flow nasal oxygen), invasive ventilation or vasopressor support.
  - b. Predicts likelihood of death.
3. Tertiary Outcomes: Successful delivery, setup, daily interface engagement, and compliance with wearing of the device

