## 5.2. Statistical Hypotheses

These study methods are designed to create an algorithm, specifically a Bayesian Network (BN), and then test the statistical accuracy of the developed Bayesian Network and comparison models on the primary and secondary outcomes. The model acceptance criteria and stated hypothesis is the model's ability to predict the primary outcome of hospitalization of study participants with 75% accuracy. The secondary outcomes will be more exploratory with less strict acceptance criteria. The ability to successfully predict secondary outcomes will largely depend on the number of secondary outcomes observed and if it warrants adequate power.

The benchmarks of model performance will be as follows: AUC between 0.50 and 0.55 is poor, 0.55 to 0.65 is moderate, 0.65 to 0.75 is acceptable, and >0.75 is excellent. Brier scores will be used to verify the accuracy of the event prediction during calibration, where a perfect score is 0 and imperfect score is 1. Brier scores will be calculated for each individual prediction, representing one study participant, and an aggregate Brier score for the sequence of predictions of the participant set.

Different specificity and sensitivity levels will need to be considered when creating a feature that automatically triggers notification of study staff to reduce number of unnecessary alarms and alarm fatigue. In addition, the duration of time a patient spends in a high-risk state needs to be considered. For example, if a participant's oxygen saturation levels (SpO2) levels decrease for a brief period, then regain to normal levels, we will evaluate this to determine if it is an indicative of

patient deterioration or not. This will likely be undertaken by generating a rolling average or median of a certain number of time periods,  $t$ , to ascertain a confident deterioration event.

If the model performs statistically significantly better than 75% (AUC >0.75) with reasonable specificity, sensitivity, and calibration the model will be finalized and deployed.

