## 6.4. Statistical Analyses and Stopping Guidance

Analyses will be conducted in three distinct parts of the trial. Analysis following the pilot study of 50 participants including feasibility, adherence rates, univariate and bivariate statistics, and informing structural design of the Bayesian Network. Descriptive statistics will include univariate analysis such as frequency, box plots, or histograms, and where appropriate, bivariate analysis on covariates using methods such as regression, Fisher's exact tests, or chi-squared analyses.

Stages 1 and 2 are covered in more depth (9.1) but generally following a training and testing machine learning design, respectively. Stopping guidance is determined by both recruitment feasibility and model performance. After a total of 2050 participants are reported, the recruitment will stop. If the model performs statistically significantly better than 75% (AUC >0.75) with reasonable specificity, sensitivity, and calibration, the model will be finalized and deployed. Benchmarks were established as reasonable for similar outcomes in literature. If the model does not meet this standard, we will conduct further analysis into where performance failures were most pervasive to decide how performance could best be improved. Adjustments to significance levels due to analysis stages are not relevant to Bayesian methods.

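### The deployment rule is an absolute AUC criterion for a mixed-input model, so meeting it would not show that the wearable data add predictive value

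*Combined protocol and SAP*

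**What the plan says.** The objective in SAP 5.1 is to "train, develop, validate and release a digital biomarker-based algorithm". The SAP preface says that demographic and in-hospital risk scores are already available and places the new tool between them: "Our algorithm might bridge the gap between demographic models and in-hospital models of disease progression by providing real-time data from the community". The protocol's Background is more direct: "A major goal of this work is to identify novel digital biomarkers".

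The hypothesis in SAP 5.2 is "the model's ability to predict the primary outcome of hospitalization of study participants with 75% accuracy", and the same section gives the release rule: "If the model performs statistically significantly better than 75% (AUC >0.75) with reasonable specificity, sensitivity, and calibration the model will be finalized and deployed". SAP 6.4 restates that rule as stopping guidance and justifies the threshold from published work: "Benchmarks were established as reasonable for similar outcomes in literature". It does not give the published AUCs.

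In SAP 9.2, Stage 2, the tested model receives demographic, medical-history, wearable and symptom variables together. The protocol's Stage 2 text says that the test participants' data "will be run through the developed Bayes network algorithm and comparison models", and SAP 5.2 also mentions comparison models. Neither document says what those models contain or how the comparison is to be made.

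**The concern.** What distinguishes this study from existing risk scores is the continuous vital-sign data. The rule looks at the total discrimination of a model that also holds age, sex, BMI, ten comorbidity and risk items (SAP 8.5) and daily symptoms. An AUC has no memory of its source: a score with a given true AUC has the same chance of passing whether or not a vital sign contributed to it. The protocol's section on the Bayesian network selects variables on the data and does not require any wearable variable to be kept.

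At stake is the interpretation of a positive result. The SAP preface foresees making the tool available at once if the study succeeds, and participants are asked to wear the device round the clock. A release under the digital-biomarker description would rest on a test that never isolates what the wearable contributes.

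**Working it through.** **The plan's own figures.** No calculation is given behind the 0.75 threshold. The sample-size figures that are given reproduce:

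- Calculation 1, in the form printed in protocol Appendix B: (1.96/0.05)² × 0.1 × 0.9 = 138.3, rounded up to 139.
- Calculation 2: exp[(−0.508 + 0.259 ln 0.1 + 0.504 ln 30 − ln 0.05)/0.544] = 755.9, against 756.
- Cohort size: 100/0.10 = 1,000.

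**Inputs.** From SAP 6.3 and 9.2: 1,000 test participants at a 10% event rate, so m = 100 events and n = 900 non-events. From SAP 7.2: alpha 0.05, taken as two-sided because sidedness is not stated. The true AUC of a non-wearable model, written A, is an assumption, so a range is shown.

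**Chance that a model without wearable data meets the AUC part.** Hanley-McNeil standard error:

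SE(A) = √{[A(1−A) + (m−1)(q1−A²) + (n−1)(q2−A²)]/(mn)}, with q1 = A/(2−A) and q2 = 2A²/(1+A).

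Chance of passing = Φ[(A − 0.75)/SE(A) − 1.96].

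| Assumed true AUC | SE | (A − 0.75)/SE | Chance of passing |
|---|---|---|---|
| 0.76 | 0.0288 | 0.35 | 5% |
| 0.78 | 0.0281 | 1.07 | 19% |
| 0.80 | 0.0272 | 1.84 | 45% |
| 0.82 | 0.0263 | 2.66 | 76% |
| 0.85 | 0.0246 | 4.07 | 98% |

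By the same standard error, a significant result needs an observed AUC of about 0.803. A simulation (4,000 runs, binormal scores, DeLong variance, two-sided) gave higher chances: 27%, 58%, 87% and over 99% at 0.78, 0.80, 0.82 and 0.85. The table is therefore not inflated by the approximation. By either method, the chance of passing the full rule can only be equal or lower, because specificity, sensitivity and calibration must also be judged reasonable.

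**What a paired comparison could detect.** With both AUCs near 0.80 (assumption) and between-model correlation r (assumption), SE of the difference = SE(0.80) × √[2(1−r)], and the gain detectable with 80% power is 2.8 times that.

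| Test set | SE(0.80) | r | SE of difference | Detectable gain |
|---|---|---|---|---|
| 100 events, 900 non-events | 0.0272 | 0.8 | 0.0172 | 0.048 |
| 100 events, 900 non-events | 0.0272 | 0.5 | 0.0272 | 0.076 |
| 50 events, 450 non-events | 0.0385 | 0.8 | 0.0244 | 0.068 |
| 50 events, 450 non-events | 0.0385 | 0.5 | 0.0385 | 0.108 |

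The smaller set is an assumption. It illustrates SAP 7.3.2, which trains and tests only on adherent participants.

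**The case against.** Several points can be made for the plan.

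- **The formal objective is prediction.** SAP 4.2 limits the scope to robustness and predictive performance, no hypothesis claims superiority over a non-wearable model, and the protocol's Background intends to combine existing algorithms with vital signs. This stands as a defence of the combined model. It does not defend the digital-biomarker label or the goal of finding such biomarkers.
- **Variable contribution is examined.** Variables are screened before entering the final model, and the protocol plans sensitivity analysis in both stages. A reader might infer that the plan would release a model with useless wearable nodes and nobody would notice. The documents do not support that: such nodes should be dropped at screening. But screening and ranking do not measure added performance in unseen participants, and neither is a release condition.
- **Comparison models are planned.** It would be wrong to say that there are none. They are undefined and outside the rule.
- **AUC is not the only condition.** Specificity, sensitivity and calibration are named too. They carry no limits and do not separate the input sources.
- **The available SAP may lack modelling detail.** Its summary of changes mentions additions, including a section 9.5, that the text does not contain. The finding is therefore limited to the text that can be read.

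The most tempting stronger reading is that demographics, comorbidities and symptoms alone would pass in this cohort. Nothing in the documents shows this. No non-wearable AUC is reported, and SAP 8.1 expects a younger sample, which could reduce discrimination by age.

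**Conclusion.** The concern holds as a statement about what the rule can show. Passing it would support the performance of the combined model and say nothing about the wearable's share. The rule permits a pass without any wearable contribution; how likely that is depends on a figure that the documents do not give. Over assumed true AUCs of 0.76 to 0.85 the chance of meeting the AUC part runs from about 5% to 98%, so the gap is minor if a non-wearable model discriminates only slightly above 0.75 and serious if it reaches about 0.82. These figures assume 100 events in 1,000 and a two-sided test. The performance analysis of the combined model is unaffected; the claim made from it is what lacks support.

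**What to change.** In SAP 5.2, 6.4 and 9.2, before Stage 2 outcomes are examined:

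1. Define one comparison model as a Bayesian network fitted in Stage 1 by the same method on demographic, medical-history and symptom variables only. Use the same participants, prediction time and data cut-off as the full model. Otherwise a baseline score would be set against up to 30 days of vital signs, and timing would be confused with added value.
2. In Stage 2, report the paired AUC difference (full minus comparator) with a 95% interval, and the Brier difference, in the same participants.
3. State in 5.2 and 6.4 that the model is described or released as digital-biomarker-based only if the lower limit of the AUC difference is above 0. Otherwise a pass on AUC >0.75 is reported as performance of the combined model only.

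The cost is SAP wording and one further model fit on data already collected. The downside is a claim that is harder to earn: the detectable gain is about 0.05 to 0.08 with 100 events and about 0.07 to 0.11 with 50 events in 500, so the SAP should add that an interval including 0 would not prove the wearable useless. Keeping symptoms in the comparator is a choice: it isolates the sensor data, whereas a comparator without symptoms would ask what the whole kit adds, since symptoms come through the study tablet.

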## 6. Study Methods

### 6.1. General Trial Design and Plan

General study design characteristics:

- Longitudinal observational cohort trial
- Virtual trial (in contrast to a single or multicenter design)
- Level and method of blinding: Participants will be aware of wearing the medical device, therefore there is no blinding to actual device wearing. However, participants will be blinded from seeing their own data being captured by the device.
- Sequence and duration of all study periods: screening, baseline, active treatment, follow-up.

### 6.2. Randomization and Blinding

No randomization will be conducted in this experiment, as it is a longitudinal observational cohort trial.

For our study participants, data will be collected “blind”. The participant will not be able to see their data in real time, and no data will be reviewed or acted upon by the study team unless there is a clinically indicated trigger elicited by the system. These triggers exist to prompt the capture of studyspecific information, not to direct participant care.

### 6.3. Sample Size

By recruiting participants that have already been identified as SARS-CoV-2/COVID-19 positive, we expect that approximately 10% of individuals from each age group will eventually develop severe or critical COVID-19 symptoms and require hospitalization or treatment in an intensive care unit. Currently there are not sufficiently rigorous statistical models for predicting statistical power for machine learning studies. Some of the issues related to sample size for machine learning models have been recently reviewed in the scientific literature. Machine learning models can be trained to find an effect, but it is not clear if the effect is the result of over-fitting and/or poor sample selection. Nested cross-validation and calibration have been proposed to mitigate these issues. Based on extensive prior experience of our group, we expect that 100 events in continuously monitored participants will be sufficient to assess the training performance of the model for early identification of novel digital biomarkers indicative of disease severity as well as future trajectory of the severity of disease. Using the 100 events and approximate 10% event

rate, we determined that testing and training cohorts of 1,000 participants each (2,000 participants total) will be sufficient.

Although not required in observational clinical trials due to no directly measured effect size, sample size calculations were conducted under different circumstances to ensure sample is sufficiently large for a clinical prediction model.

Calculation 1: Sample size required for precise estimation of the overall outcome probability in the target population. In this study a 10% event rate has been estimated. The number of participants required under the assumption this is a true event rate where  $n$  is the required sample size,  $\phi$  is the anticipated outcome proportion, and  $\delta$  is the absolute margin of error.

$$n = \left( \frac{1.96^2}{\delta} \right) \phi(1 - \phi)$$

To estimate the required number of participants to properly observe 10% event rate at margin error of  $\leq 0.05$ :

$$n = \left( \frac{1.96^2}{0.05} \right) 0.1(1 - 0.1) = 139 \text{ participants}$$

This calculation does not represent the main goal of the study, rather is the lowest bar for number of participants for the stated event observation rate.

Calculation 2: Sample size required to help ensure a developed prediction model of a binary outcome will have a small mean absolute error in predicted probabilities when applied in other targeted individuals. MAPE is the mean absolute prediction error,  $P$  is the number of candidate predictor parameters, and the constants are derived from simulations in Smeden et al. The goal of using this formula is to avoid the reductionistic “rule of 10” that would indicate the sample size required needs to be 10 times the number of parameters (in this study parameters are variables). However, using only the rule of thumb fails to account for number of categories and frequency of the category within the parameters.

$$n = \exp \left( \frac{-0.508 + 0.259 \ln(\phi) + 0.504 \ln(P) - \ln(MAPE)}{0.544} \right)$$

Given that we do not know the predictive power of a model, this estimate is conservative to apply a model to new individuals. The calculation below is given with an event rate of 0.1 (10%) ( $\phi$ ) and approximately 30 model parameters ( $P$ ) based upon our 21 variables listed in the study.

$$n = \exp \left( \frac{-0.508 + 0.259 \ln(0.1) + 0.504 \ln(30) - \ln(0.05)}{0.544} \right) = 756 \text{ participants}$$

## 6.4. Statistical Analyses and Stopping Guidance

Analyses will be conducted in three distinct parts of the trial. Analysis following the pilot study of 50 participants including feasibility, adherence rates, univariate and bivariate statistics, and informing structural design of the Bayesian Network. Descriptive statistics will include univariate analysis such as frequency, box plots, or histograms, and where appropriate, bivariate analysis on covariates using methods such as regression, Fisher's exact tests, or chi-squared analyses.

Stages 1 and 2 are covered in more depth (9.1) but generally following a training and testing machine learning design, respectively. Stopping guidance is determined by both recruitment feasibility and model performance. After a total of 2050 participants are reported, the recruitment will stop. If the model performs statistically significantly better than 75% (AUC >0.75) with reasonable specificity, sensitivity, and calibration, the model will be finalized and deployed. Benchmarks were established as reasonable for similar outcomes in literature. If the model does not meet this standard, we will conduct further analysis into where performance failures were most pervasive to decide how performance could best be improved. Adjustments to significance levels due to analysis stages are not relevant to Bayesian methods.

## 6.5. Timing of Final Analysis

We will perform the final analysis after 1000 participants in the validation phase have been observed. Final analysis will include machine learning validation and reporting. The current timeline aims to have this completed by July 30th, 2021 but is subject to changes due to study recruitment delays.

